### 3.2.2.1 Deaths, Serious and Other Significant Adverse Events

The number of subjects and their percentages with TEAEs leading to death will be summarized by MedDRA SOC and PT. A subject data listing of all AEs leading to death will be provided.

Note: A summary table will not be provided if there are no deaths in the study.

The number of subjects and their percentages with treatment-emergent SAEs will be summarized by MedDRA SOC and PT. A subject data listing of all SAEs will be provided.

The number of subjects and their percentages with TEAEs leading to discontinuation from study treatment will be summarized by MedDRA SOC and PT. A subject data listing of all AEs leading to discontinuation from study treatment will be provided.

The number of subjects and their percentages with TEAEs and the relation to study treatment will be summarized by MedDRA SOC and PT.

### 3.2.3 Clinical Laboratory Parameters

Laboratory values that are non-missing and reported as 'below the detectable limit' of an assay will be replaced by  $\frac{1}{2}^*\text{LLOQ}$ . Values that are reported as 'above the detectable limit' will be replaced by  $1.5^*\text{ULOQ}$ , to allow for summary tables to be generated. Laboratory results will be summarized using International System of Units (SI).

For all quantitative parameters listed in Section 8.1.1 of the protocol, the actual value and the change from baseline to each post-baseline visit and to the end of treatment will be summarized by visit, using descriptive summary statistics. Qualitative parameters will be summarized using frequencies (number and percent of subjects), and changes from baseline to each post-baseline visit and to end of treatment will be reported using shift tables. Percentages will be based on the number of subjects with both non-missing baseline and relevant post-baseline results.

Laboratory test results will be assigned an LNH classification according to whether the value is below (L), within (N), or above (H) the laboratory parameter's reference range. Within-treatment comparisons for each laboratory parameter will be based on 3-by-3 tables (shift tables) that compare the baseline LNH classification to the LNH classification at each post-baseline visit and at the end of treatment. Similar shift tables will also compare the baseline LNH classification to the LNH classification for the highest and lowest value during the treatment period.

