#### **4.3 Exclusion Criteria**

A potential subject who meets any of the following criteria will be excluded from participation in this study:

1. Subject has a history of any illness or any clinical condition that, in the opinion of the investigator, might confound the results of the study or pose an additional risk in administering study drug to the subject. This may include, but is not limited to, history of relevant drug or food allergies; history of cardiovascular or central nervous system disease; history or presence of clinically significant pathology; clinically significant history of mental disease; and history of cancer, except for squamous cell skin cancer, basal cell skin cancer, and Stage 0 cervical carcinoma in situ (all 3 with no recurrence for the last 5 years).
2. Subject has a known or clinically suspected infection with human immunodeficiency virus or hepatitis B or C viruses.
3. Subject has current clinically significant liver (alanine aminotransferase > 2X upper limit of normal or total bilirubin >1.5 X upper limit of normal) or kidney (GFR < 30 mL/min/1.73m^2) dysfunction.
4. Subject screens positive for hepatitis B surface antigen, hepatitis C virus (HCV) antibody, or antibodies against human immunodeficiency viruses 1 and 2 (HIV 1/HIV 2 antibodies).
5. Subject has any condition possibly affecting drug absorption (eg, gastrectomy, cholecystectomy, or other gastrointestinal tract surgery, except appendectomy).
6. Subject has a standard 12-lead ECG demonstrating QT interval by Fredericia (QTcF) >450 msec for male subjects and QTcF >470 msec for female subjects at Screening. If QTcF exceeds 450 msec for males or 470 msec for females, the ECG will be repeated 2 more times, and the average of the 3 QTcF values will be used to determine the subject's eligibility.
7. Subject has a history of cardiac dysrhythmias requiring anti-arrhythmia treatment(s); or history or evidence of abnormal ECGs that, in the opinion of the investigator or Medical Monitor, would preclude the subject's participation in the study.
8. Male subject has a female partner who is planning to become pregnant during the study or within 90 days after the last study drug dose.
9. Subject has donated blood (of approximately 1 pint [500 mL] or more) or has had any significant loss of blood within 90 days before the first study drug dose, as determined by the investigator.
10. Vaccination with a live attenuated vaccine within 6 weeks of randomisation.

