### **6.4 Summary of Known and Potential Risks and Benefits**

#### **6.4.1 Known and Potential Risks**

There are no known contraindications to the administration of losmapimod.

Losmapimod should not be administered to subjects who are hypersensitive to losmapimod or the excipients used in the losmapimod tablets.

Losmapimod should not be administered to pregnant women or women at risk of becoming pregnant because it was associated with embryo-foetal malformations in rats and rabbits.

Abnormal elevation of transaminases with or without increased bilirubin has been observed with other p38 $\alpha$  inhibitors. Although there is little evidence that this occurs with losmapimod based on the experience from previous clinical trials in over 3,500 subjects, monitoring for potential liver enzyme abnormalities is specified in the protocol as part of safety monitoring.

Clinical studies to date have not shown any consistent increase in the incidence, severity, or type of infections in subjects who received losmapimod compared to placebo. However, because of a potential modest impact of losmapimod on immune function due to inhibition of p38 $\alpha$  pharmacology, there could be circumstances when the theoretical risk of losmapimod administration may outweigh its potential benefits to subjects with FSHD1 (eg, concurrent administration with cytotoxic chemotherapy for cancer). Whether losmapimod could decrease the efficacy of immunisations has not been formally studied.

There has been no increase in renal insufficiency or renal adverse events with losmapimod

compared to placebo in previous clinical trials. However, a small increase in serum creatinine (ratio: 1.07; 95% CI, 1.02 to 1.11) was noted in 1 study, and similar trends were observed in other studies. This increase appears to attenuate with continued treatment and is reversible upon discontinuation. Losmapimod is an inhibitor of MATE1 renal transporter, which may explain this finding.

There has been no increase in cardiac arrhythmias or ECG abnormalities with losmapimod compared to placebo in the clinical trials.

Although no studies have been conducted to evaluate the potential of losmapimod for abuse and dependence, there is no reason to suspect that this will be the case based on its mechanism of action.

There are currently no identified adverse drug reactions and no expected safety risks of losmapimod that would prevent further clinical development in FSHD1 or any other indication.

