## 8. METHODS

### 8.1 Study Parameters/Endpoints

#### 8.1.1 Main Study Endpoints

Primary endpoint:

The primary endpoint is the assessment of safety and tolerability based on AEs, SAEs, clinically significant laboratory test results, ECGs, and vital signs (safety endpoint).

The secondary endpoints are as follows:

1. Changes from baseline during treatment in pHSP27 and the ratio of pHSP27/total HSP27 as measured by sorbitol stimulated peripheral whole blood (PD endpoint)
2. Changes from baseline in the ratio of pHSP27/total HSP27 in muscle during the dosing period (PD endpoint)
3. Plasma and muscle concentrations of losmapimod (pharmacokinetic [PK] endpoint)

Exploratory endpoints include changes from baseline during the dosing period in the following:

1. DUX4 activity by quantitative polymerase chain reaction (qPCR) of skeletal muscle using a subset of DUX4-regulated gene transcripts
2. Other disease transcripts by qPCR of skeletal muscle
3. Skeletal muscle lean tissue volume by whole-body MRI
4. Skeletal muscle tissue replacement by fat using whole-body MRI
5. Skeletal muscle echogenicity by ultrasound (selected muscles)
6. RWS with and without weights
7. Ambulatory function by classic and FSHD-optimised TUG
8. Physical function by MFM domain 1
9. Muscle strength by quantitative manual dynamometry
10. Disease impact by subject report using FSHD-RODS
11. Disease impact by subject report using FSHD-HI
12. Disease impact by subject report using PGIC
13. Upper and lower limb mobility in the outpatient setting using wearables
14. Change in ambulation as measured by the 6-minute walking test
15. Change in lung ventilatory function as measured by Spirometry See Table 2 for the timepoints of the assessments.

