## 1.3 MAIN STUDY ENDPOINTS

### 1.3.1 Primary Endpoint(s)

The primary endpoint is the assessment of safety and tolerability based on adverse events (AEs), serious adverse events (SAEs), clinically significant laboratory test results, electrocardiograms (ECGs) and vital signs (safety endpoints)

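### Main-study laboratory endpoint: clinically significant results have no planned count, and the Low/Normal/High shift tables cannot show worsening in a subject who is already High at baseline

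*SAP*

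**What the plan says.** **Endpoint.** Protocol 8.1.1 bases the main-study primary endpoint on AEs, SAEs and "clinically significant laboratory test results, ECGs, and vital signs (safety endpoint"; SAP 1.3.1 has the same component, "clinically significant laboratory test results, electrocardiograms (ECGs) and vital signs (safety endpoints". The extension endpoint (Protocol 8.1.2, SAP 1.4.1) refers to laboratory results without the qualifier.

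**Planned laboratory output.** For quantitative tests, SAP 3.2.3 says "the actual value and the change from baseline to each post-baseline visit and to the end of treatment will be summarized by visit". SAP 2.1 defines the statistics as mean, SD, median, minimum and maximum. Each result is "assigned an LNH classification according to whether the value is below (L), within (N), or above (H) the laboratory parameter's reference range". The comparison rule is "Within-treatment comparisons for each laboratory parameter will be based on 3-by-3 tables (shift tables) that compare the baseline LNH classification" with the class at each later visit and at end of treatment. An extreme-value version is added: "Similar shift tables will also compare the baseline LNH classification to the LNH classification for the highest and lowest value during the treatment period". Protocol 10.2.3 adds the number and percentage of out-of-range values, and a listing.

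**Windows.** SAP 2.3.5 assigns data to analysis windows and, where a window holds several visits, analyses the later one.

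**Entry and known risk.** Exclusion criterion 3 (Protocol 4.3) reads "Subject has current clinically significant liver (alanine aminotransferase > 2X upper limit of normal or total bilirubin >1.5 X upper limit of normal", with a separate GFR limit for the kidney. Protocol 6.4.1 states "Abnormal elevation of transaminases with or without increased bilirubin has been observed with other" p38-alpha inhibitors. It adds that there is little evidence of this with losmapimod in over 3,500 subjects, and that liver enzymes are monitored.

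**The concern.** The endpoint is worded in terms of clinical significance, but every planned laboratory category is cut at the reference range. Being out of range is a different thing, and the SAP knows it. For ECGs, SAP 3.2.4.3 separates abnormal findings that are clinically significant from those that are not, and adds QTc size bands. Laboratory results belong to the same endpoint and get neither.

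The Low/Normal/High scale also has a ceiling. Criterion 3 admits subjects above the upper limit for ALT or bilirubin, and no numeric limit is set for AST or CPK. For anyone who is High before dosing, the shift tables cannot tell a stable value from a large rise. At stake is whether the summary tables, without recourse to listings, can express the endpoint as worded and show the size of a change in the liver tests that the protocol says it monitors.

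**Working it through.** The plan states no figure on this point to reproduce; the sample size is declared not to rest on statistical considerations. The check applies the SAP's own rules. **All ALT values below are assumptions**, in multiples of ULN; the documents give no baseline or on-treatment laboratory data. The 14 subjects are the enrolment in Protocol 4.1.

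**1. Classification rule.** A value above 1x ULN is H; the illustrative values at or below it are N.

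| Baseline | On treatment | Fold change | Shift cell |
|---|---|---|---|
| 1.5 | 1.5 | 1.0 | H to H |
| 1.5 | 3.5 | 2.3 | H to H |
| 1.5 | 5.5 | 3.7 | H to H |
| 1.8 | 9.0 | 5.0 | H to H |
| 0.9 | 1.1 | 1.2 | N to H |

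The highest-value table uses the same classes and gives the same cells. The out-of-range count has the same ceiling. The smallest rise in the table is the only one that registers as a shift.

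**2. Descriptive statistics.** One subject goes from 1.5 to 5.5; the other 13 do not change.

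- Mean change = (5.5 - 1.5)/14 = 4.0/14 = 0.29
- SD of change = 4.0/√14 = 1.07
- Median change = 0
- Maximum change = +4.0, and the maximum value at that visit is at least 5.5

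So the maximum exposes the rise if the peak is the value analysed for that visit. It does not show that subject's baseline category.

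**3. When the peak is not the analysed value.** The Week 20, 32 and 44 windows each span 84 days (182 - 98, 266 - 182, 350 - 266). From 148 weeks post-treatment they span 168 days (for example 1120 - 952). Protocol Table 2, footnotes a and g, allows unscheduled visits and laboratory tests. Suppose a subject with baseline 1.5 has an unscheduled 5.5 after Day 98 and is back at 1.5 at the Day 140 visit. Both results fall in the Week 20 window and the later one is used.

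- By-visit value 1.5, change 0
- By-visit shift H to H
- Highest-value shift H to H
- Out-of-range before and after

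The 5.5 then appears only in the listing. If unscheduled results are not windowed at all, the outcome is the same. Had this subject started Normal, the highest-value table would at least show N to H.

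**4. Count of clinically significant results.** SAP 3.2.3 and Protocol 10.2.3 contain none, and neither document says what makes a laboratory value clinically significant. A count would give the endpoint a statement with known precision. For example, 0 of 14 has an exact two-sided 95% upper limit of 1 - 0.025^(1/14) = 23.2%.

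**The case against.** The strongest reply is that this is a 14-subject, single-arm, descriptive pilot whose outputs already expose large individual changes. The SAP reports the maximum of both values and changes at each visit and at end of treatment, the protocol adds out-of-range counts, and every laboratory value is listed. Reading 14 subjects' listings is practical. An abnormality reported as an AE would also be tabulated by severity and relatedness. Most of this stands. What remains is that the maximum is not tied to a baseline, that a peak can drop out of the by-visit tables, that a listing does not summarise a primary endpoint, and that no rule requires a laboratory finding to be reported as an AE.

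A reader might infer several stronger things that the documents do not support:

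- **That only means and shifts are planned, or that a liver signal would be missed.** Minimum, maximum and listings are planned, and a large rise would usually be seen.
- **That losmapimod carries the transaminase signal.** Protocol 6.4.1 attributes it to other inhibitors of the class and reports little evidence for losmapimod.
- **That these subjects mostly start above normal.** No baseline ALT, AST or CPK data are given, and exclusion criterion 20 screens on abnormal results by judgement.
- **That a count needs only existing data.** The documents describe an investigator assessment of clinical significance for ECGs, not for laboratory results, and GFR is not among the Table 1 tests.

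**Conclusion.** The point holds as a tabulation gap. The missing count concerns the main study only, because the extension endpoint omits the qualifier. The ceiling at High follows directly from the classification rule and applies wherever the shift tables are used. How often it matters depends on how many subjects were High at baseline, which the documents do not say.

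In the assumed example a 4.0x ULN rise leaves every shift table unchanged and moves the mean by 0.29x ULN, while the maximum shows it in full. It vanishes from all summary tables only if three things coincide: the subject is High at baseline, the peak is unscheduled, and a lower result later in the same window replaces it. Because the listings retain the data, this is a change worth considering, not a defect that undermines the safety analysis.

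**What to change.** Keep the Low/Normal/High tables and add one table to SAP 3.2.3:

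- For ALT, AST, total bilirubin, creatinine and CPK, give each subject's maximum on-treatment value over all scheduled and unscheduled results, as a multiple of ULN and of that subject's baseline, by baseline category.
- Give n (%) of subjects newly above 2x ULN for ALT, or newly above 1.5x ULN for total bilirubin. These are the protocol's own numeric terms for clinically significant liver dysfunction at entry, used here only as reporting categories and not as rules for managing subjects.
- If an investigator flag for clinical significance is captured for laboratory results, give n (%) of subjects with at least one flagged on-treatment result. If not, the sponsor should define the term, so that the endpoint and its summary match.
- Leave out a GFR row unless the SAP specifies how GFR is derived from creatinine.

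The cost is one extra safety table. All five analytes are in Protocol Table 1, so the first two items need no new data; the third depends on whether a flag exists or a definition is written.

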### **3.2.4 Vital Signs, Physical Examination Findings, and ECG**

#### **3.2.4.1 Vital Signs**

Descriptive statistics for vital signs parameters (diastolic and systolic blood pressure, pulse rate, respiration rate, temperature, weight (if collected) and changes from baseline will be presented by visit.

Vital sign results will also be assigned an LNH classification with respect to the normal ranges. Comparisons will be based on shift tables that compare the baseline LNH classification to the LNH classification at each visit. Shift tables will be used to compare the baseline LNH classification to the LNH classification for the highest and lowest value during the treatment phase.

#### **3.2.4.2 Physical Examinations**

Physical examination (PE) results are collected at screening (baseline). Each component of the baseline PE will be recorded as normal or abnormal and summarized using frequencies and percentages. Symptom-directed PE may also be performed at the discretion of the investigator. All PE data will be available in data listings.

#### **3.2.4.3 Electrocardiogram (ECG)**

ECG assessments are performed at visit 1 and visits 4-10. During the extension, ECGs are not mandatory assessments and will be carried out at the discretion of the investigator. Descriptive statistics for ECG parameters and changes from baseline will be presented.

Shift tables will present changes from baseline in ECG interpretation (categorized as normal; abnormal, not clinically significant; and abnormal, clinically significant) to end of treatment, by visit.

In addition, the number of subjects and their percentages with at least 1 post-baseline abnormal ECG result in QTc Bazett and QTc Fridericia during the treatment period will be summarized. Clinically abnormal ECG results in QTc Bazett and QTc Fridericia will be categorized as follows:

- Increase in QTc of > 60 msec from baseline
- QTc value of > 450 msec and  $\leq$  500 msec
- QTc value > 500 msec

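### The SAP's absolute QTc counts (>450 to ≤500 and >500 msec) take no account of baseline category, so an unchanged pre-dose value above 450 msec would be reported as an on-treatment abnormality

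*SAP*

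**What the plan says.** SAP 3.2.4.3 plans a summary of the number and percentage of subjects "with at least 1 post-baseline abnormal ECG result in QTc Bazett and QTc Fridericia during the treatment period will be summarized". It lists three categories, the same for both sexes and both corrections:

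- "Increase in QTc of > 60 msec from baseline";
- "QTc value of > 450 msec", with an upper limit of 500 msec inclusive;
- "QTc value > 500 msec".

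Only the increase category refers to baseline. The same section also plans descriptive statistics for ECG parameters and their changes from baseline, and shift tables. Those shift tables cover the investigator's overall reading of the tracing, not the QTc bands. Protocol 10.2.3 adds counts of out-of-range ECG values and a listing of all ECG values.

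At entry the limits differ by sex. Exclusion 6 (Protocol 4.3) excludes men with QTcF above 450 msec, and women only with "QTcF >470 msec for female subjects at Screening". It applies to QTcF alone. SAP 2.3.1 takes the last pre-dose measurement as baseline. For ECGs that is planned at Visit 4 (Protocol 8.2).

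**The concern.** ECGs are part of the primary safety endpoint (SAP 1.3.1), and the trial is open-label with one arm. No control rate shows how many subjects would fall in these bands without treatment, so the baseline value is the only reference. The two absolute bands do not use it. A pre-existing value and a new one enter the count in the same way, under a label that calls both clinically abnormal.

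The SAP handles comparable data differently elsewhere. Laboratory values (3.2.3) and vital signs (3.2.4.1) get tables of baseline class against the class of the highest and lowest on-treatment value. An adverse event that began before dosing counts as treatment-emergent only if it worsens (3.2.2). The absolute QTc bands have no such provision.

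**Working it through.** The plan gives no figure to reproduce here: the sample size has no statistical basis, and no QTc values are reported.

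**Step 1: apply the entry rule and the SAP band to the same QTcF, assuming no change on treatment.**

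| QTcF (msec) | Man eligible | Woman eligible | In >450 to ≤500 band if unchanged |
|---|---|---|---|
| 445 | yes | yes | no |
| 450 | yes | yes | no |
| 451 | no | yes | yes |
| 460 | no | yes | yes |
| 470 | no | yes | yes |
| 471 | no | no | yes |

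On QTcF, eligible women at 451 to 470 msec fall in the band with no change. No eligible man does.

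**Step 2: QTcB.** Entry does not limit QTcB, but the SAP counts it. From the two correction formulas, QTcB = QTcF × RR^(−1/6). As an illustration, take a man eligible at QTcF 440 msec with a heart rate of 75 (RR = 60/75 = 0.8 s): 440 × 0.8^(−1/6) ≈ 457 msec. He would be in the QTcB band before any dose, so the issue is not confined to women.

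**Step 3: how likely a stable subject is to be counted.** One value is enough. SAP 3.2.4.3 places ECGs at Visit 1 and Visits 4 to 10, which gives 5 post-baseline ECGs (Visits 5 to 9), or 6 with Visit 10. Assume a constant true mean μ (no drug effect) and independent normal variation. The documents give no within-subject SD, so 5, 10 and 15 msec are assumed.

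p = 1 − Φ((450 − μ)/SD), and P(at least 1 of m) = 1 − (1 − p)^m.

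For μ = 451 msec:

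| SD | p | 5 ECGs | 6 ECGs |
|---|---|---|---|
| 5 | 0.579 | 0.987 | 0.994 |
| 10 | 0.540 | 0.979 | 0.991 |
| 15 | 0.527 | 0.976 | 0.989 |

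For μ from 455 to 470 msec the probability is at least 0.993. A stable subject in this range is almost certain to be counted.

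**Step 4: size per subject.** With 14 enrolled (Protocol 4.1), and assuming all 14 were dosed and so are in the safety set: 1/14 = 7.1%; 2/14 = 14.3%.

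**Step 5: effect of a baseline condition.** If a subject must have been at 450 msec or below at baseline to count as new, a baseline of 451 to 470 msec that stays there contributes 0 instead of 1.

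**The case against.** The strongest reply is that the plan already lets a reader sort this out. A woman steady at 460 msec shows a change near zero, does not enter the category for increases above 60 msec, and has her pre-dose value in the listing. With 14 subjects, anyone can check case by case. This stands, and it limits the matter to how one table reads. A reader might infer that the SAP disregards baseline for QTc altogether. It does not: only the two absolute bands do.

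The count is also descriptive, in a study with no formal testing, and it errs towards over-reporting, which is the cautious direction for safety. That stands too. The count is inflated only if it is read as the rate of new abnormalities on treatment.

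A reader might also infer that the lower band should start at 470 msec for women to agree with exclusion 6. The documents do not support that. Nothing in them requires an entry limit and a reporting band to be equal, and exclusion 6 offers no QTcB value to match. The change could also hide a real rise: a woman going from 415 to 470 msec (+55) would enter no category, whereas the SAP as written counts her.

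**Conclusion.** The point holds as a minor reporting weakness. The absolute QTc counts mix pre-existing with new values, and the entry rules allow pre-existing values above 450 msec: QTcF in women up to 470 msec, and QTcB in either sex. Each unchanged subject of this kind adds 7.1 percentage points at N = 14.

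That is a size per case, not an estimate of actual inflation. A reader might infer that women at 451 to 470 msec are in fact being counted, or that the primary safety result is overstated by 7 or 14 points. The documents do not show this. They give neither the number of women enrolled nor any QTc value. Eligibility rests on the Screening ECG, while baseline is planned at Visit 4, and exclusion 7 lets the investigator exclude for an abnormal ECG. The number affected may be zero.

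The probabilities in the working rest on the assumed SDs, normality and independence. The mismatch between the entry rule and the band does not.

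**What to change.** Keep the 450, 500 and >60 msec thresholds and the existing count. Add to SAP 3.2.4.3, separately for QTcF and QTcB:

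- a shift table of baseline category (≤450, >450 to 500, >500 msec; baseline as in SAP 2.3.1) against the category of the highest post-baseline value, following the approach in SAP 3.2.3 and 3.2.4.1;
- a line with the number and percentage of subjects newly entering each category;
- the display by sex.

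No change to the eligibility limits is implied.

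The cost is one extra table and its wording. The newly-entering line has two limits. It omits rises within a category, such as 455 to 500 msec (+45), which is why the overall count and the change summaries must stay. It also compares one baseline value with the worst of several. Under the Step 3 assumptions, a subject with a true mean of 445 msec exceeds 450 at least once in 5 ECGs with probability 0.578 (SD 5) to 0.900 (SD 15). A new entry is therefore not in itself evidence of a drug effect and should be read beside the change from baseline.
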